#### 11.2.2.4 Serious Adverse Event Collection Time Frame

All SAEs, regardless of the relationship to study, are collected from the time the subject signs the informed consent until the End of Study/Early Termination Visit. The investigator or designee must report all SAEs promptly to CRO within 24 hours of first becoming aware of the event.

Any SAE(s), regardless of relationship to study, which occurred during the study but is not discovered by the site until after the study has been completed must be reported to CRO within 24 hours of the first awareness of the event. Please see individual study site documentation (study binder) for forms and contact details.

#### 11.2.2.5 Serious Adverse Event Onset and Resolution Dates

The onset date of the SAE is defined as the date the event meets serious criteria. The resolution date is the date an outcome is reached or stabilization is achieved (i.e. the investigator does not expect any further improvement or worsening of the event).

Any signs or symptoms experienced by the subject after signing the informed consent form and assent form (if applicable) or leading up to the onset date of the SAE or following the resolution date of the SAE must be recorded as an AE.

### 11.2.3 Fatal Outcome

Fatal should only be selected as an outcome when the AE results in death. If more than 1 AE is possibly related to the subject's death, the outcome of death should be indicated for each such AE.

Any AE that results in the subject's death must have fatal checked as an outcome with the date of death recorded as the resolution date. AEs resulting in death must be reported within 24 hours as a SAE, if not already reported as such. In the event of a subject's death, data should be collected on whether the death occurred after the withdrawal of care and, if so, the reason for the withdrawal of care.

For other AEs, ongoing at the time of death that did not contribute to the subject's death, the outcome should be considered not resolved, without a resolution date recorded.

## 11.3 Special Considerations

### 11.3.1 Pregnancy

All females of childbearing potential, and males with female partners of childbearing potential, who participate in the study should be counseled on the need to utilize a highly effective method of birth control throughout the study and for 28 days following the last dose of study drug, and on the importance of avoiding pregnancy during study participation. A highly effective method of birth control is defined as one that results in a low failure rate (i.e., <1% per year) when used consistently and correctly, such as oral/injectable/inserted/implanted/ transdermal contraceptives, condom with diaphragm, condom with spermicide, diaphragm with spermicide, intrauterine hormone-releasing system or IUD, or sexual abstinence. Contraception is not required where at least 6 weeks have passed since sterilization, defined as females having undergone one of the following surgeries: hysterectomy, bilateral tubal ligation or occlusion, bilateral oophorectomy, or bilateral salpingectomy; and males who are vasectomized. Contraception is not required where females are postmenopausal (12 consecutive months of spontaneous amenorrhea and age  $\geq 51$  years).

Females and males with female partners should be instructed to contact the investigator or study staff immediately if pregnancy occurs or is suspected.

Pregnancy testing will be conducted on every female as per the schedule of assessments ([Table 1](#)). A female who is found to be pregnant at screening will be excluded from the study and considered to be a screening failure. A female who is found to be pregnant after receiving investigational product is required to be discontinued from the study and the end of study visit assessments performed as soon as possible after learning of the pregnancy.

The investigator must report the pregnancy of any female (study participant or female partner of male study participant) who becomes pregnant during investigational product treatment or within 28 days of discontinuing the investigational product (permission must be obtained from the pregnant female partner of a male subject to follow the pregnancy to conclusion and report the results). The pregnancy must be reported within 24 hours of learning of the pregnancy to the CRO

using the Pregnancy Data Collection Form via the same email address as for SAE reporting. The investigator should contact the designated individual(s) who receive pregnancy notification and record information related to the pregnancy on the Pregnancy Form/other designated form provided by the Sponsor or its designee.

The investigator is also responsible for following the pregnancy until delivery or termination. These findings must be reported on the Pregnancy Data Collection Form and forwarded to the designated individual(s). The event meets the SAE criterion only if it results in a spontaneous abortion or a congenital anomaly.

### **11.3.2 Reporting to Regulatory Agency, Institutional Review Board/Ethics Committee (EC) and Site**

The Sponsor or its designee is responsible for notifying the relevant regulatory authorities and if applicable, US central institutional review board (IRB) of related, unexpected SAEs.

In addition, the Sponsor and the CRO are responsible for notifying active sites of all related, unexpected SAEs occurring during all interventional studies across the development program.

The investigator is responsible for notifying the local IRB, local ethics committee (EC), or the relevant local regulatory authority of all SAEs that occur at his/her site, as required.

## **12 STATISTICS**

### **12.1 Sample Size Determination**

The sample size in this study will be approximately 80 with 40 subjects per treatment arm, randomized in a 1:1 ratio.

The sample size estimate was based on the estimated proportions of patients in the two treatment groups expected to have an asthma related event as defined by the primary endpoint. In a study with another product, rates of 6% in the active group and 44% in the placebo group were observed (Wenzel, 2013). If these estimates were used as is, then a study with 40 subjects per group would have over 95% power. Considering likely variations from the cited study, estimates of sample were assessed assuming a Type I error of 5% and the proportion of subjects with an asthma related event ranging from 30% to 50% in the placebo group and 5% to 8% in the active group. In the 20 such scenarios examined, only in the cases in which the difference between treatments gets below 23% does the power fall slightly below 80%. In the vast majority of cases examined the power is greater than 90%.

A sample size re-estimation may be performed at a point in time when an adequate number of subjects has been enrolled to provide meaningful data. Details will be provided in the statistical analysis plan.

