STATISTICAL METHODS	
For the primary variable, comparison of the proportions of subjects that had an asthma-related event will be via a Wald Z-test (continuity corrected). Summary statistics will be provided via a 2x2 table showing the number and percentage with and without asthma-related events in each treatment group. The test statistic, its associated p-value and a 95% confidence interval for the treatment difference will also be provided.
 
All other efficacy variables will be summarized using descriptive statistics. Descriptive statistics for continuous data will include number of subjects (n), mean, standard deviation, median, minimum, and maximum. Summaries of change from baseline variables will include only subjects who have both a baseline value and corresponding value at the timepoint of interest. Descriptive statistics for categorical data will include frequencies and percentages.
 
AE data will be coded using the Medical Dictionary for Regulatory Activities (MedDRA). The overall incidence of subjects having at least one AE will be summarized. The incidence of treatment-emergent adverse events (TEAEs) will be summarized by treatment group, system organ class (SOC), and preferred term (PT). Each subject will be counted only once per SOC and PT. For all continuous safety variables (e.g., laboratory and vital sign measures), descriptive statistics for all reported values and change from baseline values will be summarized by treatment group.

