SAMPLE SIZE DETERMINATION	The sample size in this study will be approximately 80 with 40 subjects per treatment arm, randomized in a 1:1 ratio. The sample size estimate was based on the estimated proportions of patients in the two treatment groups expected to have an asthma related event as defined by the primary endpoint. In a study with another product, rates of 6% in the active group and 44% in the placebo group were observed ( Wenzel, 2013 ). If these estimates were used as is, then a study with 40 subjects per group would have over 95% power. Considering likely variations from the cited study, estimates of sample were assessed assuming a Type I error of 5% and the proportion of subjects with an asthma related event ranging from 30% to 50% in the placebo group and 5% to 8% in the active group. In the 20 such scenarios examined, only in the cases in which the difference between treatments gets below 23% does the power fall slightly below 80%. In the vast majority of cases examined the power is greater than 90%.
STUDY AND TREATMENT DURATION	
After the Screening visit, subjects will complete a 30-day, stable therapy, run-in until randomization at the Baseline Visit (Day 0). AVTX-002 or placebo will be administered at Visit 2 (Day 0), Visit 5 (Day 28), and Visit 7 (Day 56). The final visit will be on Day 98.
 
The overall study duration will be up to approximately 135 days.

Table 1: Schedule of Assessments

Procedure	Screening	30-Day Run-In Period	Baseline	Double-Blind Treatment Period									
				Visit 1	Visit 1a	Visit 2	Visit 3	Visit 4	Visit 5	Visit 6	Visit 7	Visit 8	Visit 9 / ET 
Visit													
Assessment Week	-4			-1	0	1	2	4	6	8	12	14	
Assessment Day		Approximately -30 through -37 		0	7	14	28	42	No later than 56 	84	98		
Visit Window 	NA		-2 days	+3 days 	±1 day	±1 day	±3 days	±3 days	-3 days	±3 days	±3 days		
Immunophenotyping of circulating immune cells				X						X		X 	
Sputum: soluble LIGHT and gene expression 				X						X			
Plasma: AVTX-002 level				X	X	X	X	X	X	X		X 	
Clinical laboratory tests (hematology, clinical chemistries)	X			X	X	X	X	X	X	X		X	
Urinalysis	X			X	X	X	X	X	X	X		X	
Serum pregnancy test 	X			X	X	X	X	X	X	X			
Urine pregnancy test 				X	X	X	X	X	X	X			
Study drug administration (onsite) 				X	X	X	X	X	X	X			
Salmeterol/Fluticasone Run-In													

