#### **12.3.5 Efficacy Analyses**

For the primary variable, comparison of the proportions of subjects that had an asthma related event will be via a Wald Z-test (continuity corrected). Summary statistics will be provided via a 2x2 table showing the number and percentage with and without events in each treatment group. The test statistic, its associated p-value and a 95% confidence interval for the treatment difference will also be provided.

All other efficacy variables will be summarized using descriptive statistics. Descriptive statistics for continuous data will include number of subjects (n), mean, standard deviation, median, minimum, and maximum. Summaries of change from baseline variables will include only subjects who have both a baseline value and corresponding value at the timepoint of interest. Descriptive statistics for categorical data will include frequencies and percentages.

Further details regarding all statistical analysis can be found in the study Statistical Analysis Plan (SAP).

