Version: Final 4.0	
Update to Section 6.2.4 for imputation of missing values and derivation of overall score for the Asthma Control Questionnaire
 
Update to Section 10.3 to add that the screening eosinophil level will be part of the subject listing as well as table summary for demographics and baseline characteristics
 
Update to Section 10.6.1 to add that Wald Ztest will be performed including and without continuity correction
 
Update to Table 4 (Appendix 2) to clarify imputation of missing start date for prior and concomitant medications
 
Update to Table 9 (Appendix 5) to add CTCAE grading for laboratory parameters analyzed per protocol

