6.1.1 Justification of Sample Size

The sample size in this study will be approximately 80 subjects, ie, 40 subjects per treatment arm, randomized in a 1:1 ratio.

The sample size estimate was based on the estimated proportions of subjects in the 2 treatment groups expected to have an asthma related event as defined by the primary endpoint. In a study of similar design with another asthma controller therapy, rates of 6% in the active group and 44% in the placebo group were observed [3]. If these estimates were used as is, then a study with 40 subjects per group would have over 95% power. Considering likely variations from the cited study, estimates of sample were assessed assuming a Type I error of 5% and the proportion of subjects with an asthma related event ranging from 30% to 50% in the placebo group and 5% to 8% in the active group. In the 20 such scenarios examined, only in the cases in which the difference between treatments gets below 23% does the power fall slightly below 80%. In the vast majority of cases examined the power is greater than 90%.

The overall event rate may be assessed in a blinded fashion when an adequate amount of subject followup has occurred. If this event rate is found to be much lower than assumed, a sample size reestimation may be performed.

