8 CHANGES IN CONDUCT OR PLANNED ANALYSES FROM THE PROTOCOL

The following changes from protocol conventions are applied:

1.

According to the Schedule of Assessments (Table 1 in study protocol), numbering of assessment day starts at Day 0 at Visit 2, Baseline; ie:

Procedure	Screening	...	Baseline		Doubleblind Treatment Period					
Visit	V 1	...	V 2	V 3	V 4	V 5	V 6	V 7	V 8	V 9/ET
Assessment Week	-4	...	0	1	2	4	6	8	12	14
Assessment Day	Appr -37	...	0	7	14	28	42	No later than 56	84	98

Appr = approximately; ET = early termination; V = Visit

For the purpose of presentation of the study results however, the first day of dosing will be denoted Day 1 (ie, there will be no Day 0). This results in the following changes to numbering of assessment day, according to which the study results will be reported:

Procedure	Screening	...	Baseline		Doubleblind Treatment Period					
Visit	V 1	...	V 2	V 3	V 4	V 5	V 6	V 7	V 8	V 9/ET
Assessment Week	-4	...	0	1	2	4	6	8	12	14
Assessment Day	Appr -37	...	1	8	15	29	43	No later than 57	85	99

Appr = approximately; ET = early termination; V = Visit

2.

According to protocol Section 11.1.1, an AE will be considered treatmentemergent if it occurs after the first dose of investigational product and within 28 days after a subject's last dose of investigational product. However, since the start time for AEs are collected in this study only if AE duration is < 24 hours, the definition for an AE to be considered treatmentemergent will be as follows:

- If AE start time is recorded: an AE will be considered treatmentemergent if it occurs on or after the time of first dose of investigational product and within 28 days after a subject's last dose of investigational product.
- If AE start time is not recorded: an AE will be considered treatmentemergent if it occurs on or after the date of first dose of investigational product and within 28 days after a subject's last dose of investigational product.

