10.6.1 Primary Endpoint Analysis

The primary endpoint analysis is performed using the assessments for the occurrence of asthma related events based on programmatic derivations from raw data.

The proportion of subjects who experience any asthma related event will be summarized by treatment group, also including the proportion of subjects who experience each of the 5 separate criteria for an asthma related event (as identified in [Section 6.2.1](#)). A subject who experienced multiple asthma related events will be counted once in each of the applicable criteria categories and once for having an asthma related event.

Summary statistics showing the number and percentage of subjects with and without asthma related events in each treatment group will be provided via a 2x2 table. Comparison of the proportions of subjects who had an asthma related event will be via a Wald Z-test (including and without continuity correction). The test statistic, its associated p-value and a 95% confidence interval for the treatment difference will also be provided.

The summary table and associated statistical analysis of the occurrence of asthma related events will be repeated for results obtained using each of the 4 baseline values for mean daily number of SABA puffs/inhalations and mean peak flow rate calculated according to Definitions 1 to 4 in [Section 9.2](#), for all subjects in the FAS. In addition, the results for occurrence of asthma related events using the baseline values for mean daily number of SABA puffs/inhalations and mean peak flow rate calculated according to Definition 1 in [Section 9.2](#), for subjects in the Per Protocol Analysis Set, will also be presented.

Figures (one per subject) will display the % change from baseline in peak flow rate and change from baseline in daily number of SABA puffs/inhalations over time. Baseline values calculated according to Definition 1 in [Section 9.2](#) will apply. Occurrence of the following will also be

indicated on the figure for each subject: administration of each dose of study drug, reduction of fluticasone dose, discontinuation of salmeterol and fluticasone, end of study participation. As part of the figure, information on subject disposition (whether the subject completed the study or reason for early discontinuation from the study) and whether any criteria for occurrence of an asthma related event were met, will also be displayed.

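### The sample size text names no test or sidedness, its 23-point power boundary is not met by the protocol's continuity-corrected test read two-sided, and the SAP does not say whether the corrected or uncorrected test decides

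*Protocol*

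**What the plan says.** Protocol 12.1 plans 40 subjects per arm. Of its significance level it says only that "estimates of sample were assessed assuming a Type I error of 5" percent (the synopsis has the same words). It cites event rates of 44% on placebo and 6% on active from another product, for which it claims power above 95%. It then varies placebo from 30% to 50% and active from 5% to 8% over 20 scenarios and concludes that "only in the cases in which the difference between treatments gets below 23% does the power fall slightly below 80" percent. SAP 6.1.1 repeats this and adds, as the protocol does: "In the vast majority of cases examined the power is greater than 90" percent. None of the three places names a test, a sidedness or a variance form.

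The protocol names one primary test. Section 12.3.5 says that "comparison of the proportions of subjects that had an asthma related event will be via a Wald Z-test (continuity corrected"), reported with a 95% confidence interval; the synopsis agrees.

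SAP 10.6.1 says the comparison "will be via a Wald Z-test (including and without continuity correction"). It then asks for a test statistic and p-value in the singular. The version history for SAP Final 4.0 (02 Jun 2023) records the origin: "Update to Section 10.6.1 to add that Wald Ztest will be performed including and without continuity correction". SAP Section 8 opens with "The following changes from protocol conventions are applied" and lists two items, the numbering of study days and the definition of treatment-emergent events. The second version of the primary test is not among them.

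**The concern.** There are two linked gaps.

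The first is the decision rule. The protocol commits to one version of the test and the SAP produces two p-values without saying which one determines success. Protocol 12.3 leaves analytical detail to the SAP, so the protocol's wording alone does not clearly settle it. With 40 per arm and few events on active, the correction is large enough to move a result across 0.05. If the choice is still open at unblinding, the primary result can be called either way.

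The second is the power statement. If the analysis is the corrected test at two-sided 5%, the stated 23-point boundary is too favourable when the placebo rate is near 30%. The safeguard in SAP 6.1.1, a blinded look at the overall event rate, is optional and has no trigger value. The overall rate would be (30 + 7)/2 = 18.5% at 30% v 7%, against (44 + 6)/2 = 25% at the cited rates.

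**Working it through.** **Inputs.** From protocol 12.1: n = 40 per arm; type I error 5%; reference rates 44% v 6%; placebo 30–50%, active 5–8%; 20 scenarios. From protocol 12.3.5: Wald Z-test, continuity corrected, with a 95% interval.

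**Assumptions.** The 5% is two-sided (one-sided 5% is also computed). The 20 scenarios are placebo 30/35/40/45/50% by active 5/6/7/8%, which gives 5 × 4 = 20. The correction is (1/2)(1/40 + 1/40) = 0.025.

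**Step 1: can the stated boundary be reproduced?** Take 30% v 7%, a 23-point difference, with unpooled variance and the normal approximation:

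- SE = √(0.30 × 0.70/40 + 0.07 × 0.93/40) = √(0.00525 + 0.0016275) = 0.0829
- Two-sided, uncorrected: 0.23/0.0829 − 1.960 = 0.81, power 79.2%
- One-sided 5%, corrected: (0.23 − 0.025)/0.0829 − 1.645 = 0.83, power 79.6%
- Two-sided, corrected: (0.23 − 0.025)/0.0829 − 1.960 = 0.51, power 69.6%

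The first two fit the plan's boundary to within a point. The third, which is the protocol's test read two-sided, misses it by about 10 points.

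**Step 2: exact power.** All 41 × 41 possible outcomes are weighted by their binomial probabilities, and power is the total probability of those with p < 0.05. Power in %, by placebo v active rate:

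| Test | 30 v 5 | 30 v 6 | 30 v 7 | 30 v 8 | Scenarios <80% | Scenarios >90% | 44 v 6 |
|---|---|---|---|---|---|---|---|
| Two-sided, uncorrected, unpooled | 88.8 | 84.5 | 79.6 | 74.4 | 2 | 15 | 99.1 |
| One-sided 5%, corrected, unpooled | 88.9 | 84.9 | 80.6 | 75.8 | 1 | 15 | 99.2 |
| One-sided 5%, corrected, pooled | 88.4 | 84.1 | 79.4 | 74.2 | 2 | 15 | 99.1 |
| Two-sided, corrected, unpooled | 82.1 | 76.8 | 71.1 | 65.2 | 3 | 13 | 98.2 |
| Two-sided, corrected, pooled | 78.5 | 72.7 | 66.8 | 60.9 | 5 | 13 | 97.8 |

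For the two-sided corrected test, power is already below 80% at 24 and 23 points under either variance form. In the unpooled form all three failures are at 30% placebo; the lowest value at 35% is 81.3% (35 v 8). In the pooled form 35 v 8 also fails, at 78.4%. The claim of more than 95% at 44 v 6 holds on every reading.

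**Step 3: how often do the two SAP versions disagree?** Take 10/40 placebo v 3/40 active, a difference of 0.175.

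- Unpooled SE = √(0.25 × 0.75/40 + 0.075 × 0.925/40) = 0.0801. Uncorrected z = 0.175/0.0801 = 2.18, p = 0.029. Corrected z = 0.150/0.0801 = 1.87, p = 0.061.
- Pooled variance gives p = 0.034 and 0.069.

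The probability that exactly one version has two-sided p < 0.05, at 30% placebo with 5–8% active, is 6.8–9.2% (unpooled) or 10.3–13.5% (pooled). At 44 v 6 it is 0.8% and 1.3%.

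**Step 4: type I error.** Scanning common event rates from 1% to 99%, the uncorrected test peaks at 5.9% (common rate near 9%). The corrected test never exceeds 3.3%.

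**The case against.** **The power statement is not shown to be wrong.** The sample size text names no test, and its boundary is within half a point of the two-sided uncorrected Z-test. The discrepancy appears only after importing the correction from another section and inferring two-sidedness and the grid. This stands as a limit: the finding is conditional. But neither reading that fits is satisfactory as written. One is not the protocol's test; the other has to be reconciled with the 95% interval.

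**The analysed number may exceed 40 per arm.** The target is 80 completers (protocol 8.1), while efficacy uses all dosed subjects with a baseline and a post-baseline value, and the protocol takes some subjects with events out of the study. If no subject with an event completed, 80 completers at an 18.5% event rate would imply 80/0.815 ≈ 98 dosed, or 49 per arm. Unpooled corrected power is then 86.8%, 82.0% and 76.6% at 24, 23 and 22 points, close to the stated boundary. That is an extreme assumption, the pooled form still gives 79.7% at 23 points, and the plan's own text rests on 40 per group. At 44 per arm the 23-point power is 76.7%; it first reaches 80% at 47.

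**The consequences are small at the planning rates.** At 44 v 6 the versions disagree in about 1% of trials. The 5.9% type I maximum lies at a common rate below every overall rate in the grid (17.5–29%); at 25% the uncorrected test is at 5.35% unpooled and 5.0% pooled. This is correct. The case rests on an undefined decision rule more than on type I inflation.

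**The protocol's test governs by default.** The SAP history speaks of adding a version, so the corrected test could be presumed still primary. That is a reasonable reading, but it is not written. The SAP ranks alternatives elsewhere, labelling one of its four baseline definitions as primary, and does not do so here.

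**Conclusion.** The concern holds. The undefined decision test is the part that must be settled before unblinding: SAP 10.6.1 gives two versions of the primary test, and a result such as 10/40 v 3/40 is significant on only one of them. Type I error exceeds 5% only if the uncorrected version is allowed to decide, and then only slightly.

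The power point is secondary and conditional. Assuming two-sided 5%, 40 per arm and the inferred 5 × 4 grid, the protocol's corrected test has 71.1% power (unpooled) or 66.8% (pooled) at the 23-point boundary. At 22 points it has 65.2% or 60.9%, which is more than slightly below 80%. It exceeds 90% in 13 of 20 scenarios. In the unpooled form 17 of 20 scenarios keep at least 80%, so the planned size is adequate unless the placebo rate is close to 30%.

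**What to change.** 1. In SAP 10.6.1, name the continuity-corrected Wald Z-test at two-sided 5%, in the Full Analysis Set with baseline Definition 1, as the single decision test. State whether its variance is pooled or unpooled. Label the uncorrected test supportive and list its addition in SAP Section 8.

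2. In the synopsis, protocol 12.1 and SAP 6.1.1, state the test, sidedness and variance form, and replace the 23-point and vast-majority sentences with power for that test. For the two-sided corrected test with 40 per arm:
   - unpooled: 65–82% at 30% placebo, 81–92% at 35%, at least 91% at 40% or more;
   - pooled: 61–79%, 78–90% and at least 90%;
   - either form: 13 of 20 scenarios above 90%.

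   If one-sided 5% was intended, say so and reconcile it with the 95% interval.

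The first change needs only a SAP revision and is the urgent one. The second adds no patients, but changing the protocol text needs a formal amendment with investigator signature and IRB approval (protocol 13.6). Its other cost is a less favourable stated power at low placebo rates.
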